#### 9.7.1.8.3 LABORATORY VALUES

Laboratory results will be summarized using Système International (SI) units, as appropriate. For all quantitative parameters, the actual value and the change from baseline to each postbaseline visit will be summarized by visit using descriptive statistics. Qualitative parameters will be summarized using frequencies (number and percentage of subjects).

Percentages will be based on the number of subjects with both nonmissing baseline and at least 1 postbaseline results.

Laboratory parameters will be categorized according to CTCAE v4.03 grades, and shift tables from baseline CTCAE grades to the maximum/worst and final postbaseline grades will be provided.

#### 9.7.1.8.4 VITAL SIGNS

Descriptive statistics for vital signs parameters (ie, systolic and diastolic BP, heart rate, respiratory rate, temperature, weight) and changes from baseline will be presented by visit.

#### 9.7.1.8.5 ELECTROCARDIOGRAMS

Descriptive statistics for ECG parameters and changes from baseline will be presented by visit. Change from baseline to each postbaseline visit and to end of treatment in ECG findings will be summarized by visit.

#### 9.7.1.8.6 OTHER SAFETY ANALYSES

Descriptive statistics and changes from baseline for LVEF assessed on echocardiogram or MUGA scans will be presented.

#### 9.7.1.9 Other Analyses

PRO-CTCAE questionnaire results will be summarized descriptively.

### 9.7.2 Determination of Sample Size

With the sample size of 100 subjects, assuming that more than 50% subjects will go on to receive TPC, and that the rate of TEAE with CTCAE Grade  $\geq 3$  is 75%, the half width of 95% CI for the rate of TEAE with CTCAE Grade  $\geq 3$  will be no more than 12%.

**Table 4** provides the 95% CI estimates for the rate of TEAEs with CTCAE Grade  $\geq 3$ , when the percentages of subjects receiving TPC range from 100% to 50%.

**Table 4 Half width of 95% CI estimates for Rate of TEAE with CTCAE Grade $\geq 3$  for Subjects Receiving TPC (Range from 100% to 50%)**

Percentage of subjects receiving TPC	The half width of 95% CI for the rate of TEAE with CTCAE Grade $\geq 3$
100%	8.5%
90%	8.9%
80%	9.5%
70%	10.1%
60%	11%

50%	12%
-----	-----

CI = confidence interval, CTCAE = Common Terminology Criteria for Adverse Events, TEAE = treatment emergent adverse events, TPC = treatment of physician choice

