**Sample Size Rationale**

With the sample size of 100 subjects, assuming that more than 50% of subjects will go on to receive TPC, and that the rate of TEAE with CTCAE Grade  $\geq 3$  is 75%, the half width of the 95% CI for the rate of TEAE with CTCAE Grade  $\geq 3$  will be no more than 12%.

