Lenvatinib (LENVIMA®) is a kinase inhibitor that was approved by FDA for the treatment of patients with locally recurrent or metastatic, progressive, radioactive iodine-refractory differentiated thyroid cancer as well as for the treatment of advanced renal cell carcinoma in combination with everolimus following one prior anti-angiogenic therapy.

The recently concluded Study E7080-G000-304 (REFLECT) [Study 304] investigated the effect of lenvatinib vs sorafenib in subjects with HCC. Sorafenib is the standard of care for first-line treatment of advanced HCC. Study 304 was a multicenter, randomized, open-label, noninferiority Phase 3 study comparing the efficacy and safety of lenvatinib versus sorafenib as a first-line systemic treatment in subjects with unresectable HCC (uHCC). Study 304 is a positive study with an adequately defined non-inferiority margin and valid assay sensitivity that met its primary endpoint showing that OS with lenvatinib was noninferior to sorafenib. Lenvatinib also demonstrated statistically significant and clinically meaningful improvement for all secondary efficacy endpoints (PFS, time to progression [TTP] and ORR) (Cheng, et al., 2017).

Post-progression therapy may have affected survival in both arms and especially in the sorafenib group as more subjects received post-treatment anticancer therapy in the sorafenib arm than in the lenvatinib arm, particularly in the Western region. After study treatment, subjects on the sorafenib arm were eligible for second-line studies targeting enrollment of sorafenib failures and/or sorafenib-intolerant subjects, while subjects on the lenvatinib arm were not.

Initial clinical experience with lenvatinib in advanced HCC was obtained in a Phase 1/2 clinical study (E7080-J081-202). The recommended Phase 2 dose was determined to be

12 mg for HCC subjects with Child-Pugh Class A. In subjects with Child-Pugh scores of 7-8, the maximum tolerated dose (MTD) was 8 mg once daily (QD). In Study 304, lenvatinib had an acceptable safety profile in HCC subjects when treatment was initiated at 8 mg or 12 mg QD (based on body weight [BW]) and adjusted by a dose-reduction algorithm to manage toxicity ([Study E7080-G000-304 Clinical Study Report, 2017](#)). Results from Study 304 provide evidence for lenvatinib as a potential effective and safe first-line treatment for patients with HCC.

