## 7.1 Study Rationale

Since 2007 there has been only 1 approved systemic medication (sorafenib) for patients with uHCC. Because of this fact in the treatment landscape, studies that evaluated second line treatment of HCC required prior sorafenib as first line therapy. Therefore, the currently approved second line medications (regorafenib and nivolumab) were studied as subsequent sequential therapies to sorafenib. Results from the phase 3 REFLECT study (Study 304) demonstrated the treatment effect of lenvatinib on OS, which was statistically confirmed by non-inferiority to sorafenib for first-line treatment for patients with uHCC. Therefore, it is important to address unmet medical need for data for safety and efficacy on the subsequent sequential therapies after 1st line therapy with lenvatinib in uHCC patients.

The safety and efficacy of lenvatinib in first line uHCC has been established in the large Phase 3 international REFLECT study. This has led to the approval of lenvatinib as first line treatment in uHCC in Japan, EU and in the US. In the REFLECT study, upon progression with first line lenvatinib, 32.6% of patients received subsequent anticancer medications. The information on safety of the subsequent medications after lenvatinib was not captured in the REFLECT study, since patients on lenvatinib were followed post-progression only for OS. Therefore, the objective of study E7080-M001-222 is to capture the safety and tolerability of the subsequent sequential therapy after first-line lenvatinib in patients with uHCC.

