The survival follow-up from Study 304 has shown some preliminary information of subsequent treatment following the first-line lenvatinib treatment in HCC subjects during the study period (01 Mar 2013 to 13 Nov 2016). During survival follow-up in Study 304, the percentage of subjects receiving post-treatment anticancer medications (not given for a procedure) in the lenvatinib arm compared with sorafenib arm was 32.6% vs 38.7%, respectively. Sorafenib was the most common anticancer agent given to lenvatinib-treated subjects during survival follow-up, taken by 25.3% of subjects; 11.8% of sorafenib-treated subjects restarted or continued sorafenib during survival follow-up. The percentage of subjects who took investigational anticancer drugs during survival follow-up in the lenvatinib arm compared with the sorafenib arm was 3.1% vs 9.5%, respectively. These investigational agents were mostly administered within clinical trials (eg, regorafenib, cabozantinib), which

required failure of sorafenib therapy as an entry criteria, thus precluding enrollment of lenvatinib-treated subjects in these studies ([Study E7080-G000-304 Clinical Study Report, 2017](#)).

This is a single-arm, open-label, multicenter, Phase 2 study to evaluate the safety and efficacy of subsequent systemic treatment of physician choice (TPC) (commercially available) following first-line lenvatinib treatment for uHCC.

The primary objective of the study is to evaluate the safety and tolerability of subsequent systemic TPC following first-line lenvatinib treatment in uHCC subjects. The secondary objectives include evaluation of OS in uHCC subjects treated with lenvatinib as first-line treatment followed by TPC, and evaluation of PFS and TTP of subsequent systemic TPC starting from the first dose of first-line lenvatinib treatment.

Approximately 100 subjects will be enrolled to first-line treatment with lenvatinib. Subjects with Child-Pugh A will be included in this study. Starting dose of lenvatinib will be based on baseline BW: 12 mg QD or 8 mg QD will be orally administered for subjects' BW  $\geq 60$  kg or  $< 60$  kg, respectively.

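### Should the N=100 justification be extended below 50% TPC uptake, given that Study 304 saw 32.6% go on to further medication?

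*Combined protocol and SAP*

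**What the plan says.** Section 9.7.2 gives the whole sample size argument. With 100 subjects, "assuming that more than 50% subjects will go on to receive TPC", and a true rate of 75% for TEAEs of Grade 3 or higher, the 95% confidence interval is to have a half-width of no more than 12%. The synopsis (Sample Size Rationale) repeats the condition: "assuming that more than 50% of subjects will go on to receive TPC". Table 4 then lists the half-width "when the percentages of subjects receiving TPC range from 100% to 50" per cent, in six rows: 8.5, 8.9, 9.5, 10.1, 11 and 12%.

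Section 7.1 reports what happened in Study 304. It says that "upon progression with first line lenvatinib, 32.6% of patients received subsequent anticancer medications". A second account begins "During survival follow-up in Study 304, the percentage of subjects receiving post-treatment anticancer medications" and gives 32.6% for the lenvatinib arm and 38.7% for the sorafenib arm.

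In the present study TPC is a planned second treatment period (sections 9.1 and 9.4.3). Subjects whom the investigator judges unsuitable for commercially available systemic therapy go to survival follow-up instead (sections 9.1.2.2 and 9.4.1.2).

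**The concern.** The primary endpoint is safety during TPC, so the informative sample is the number who reach TPC and not the 100 enrolled. The only precision figure offered for that endpoint rests on an uptake above one half, for which no source is given. Both overall uptake figures in section 7.1 are below one half, and Table 4 stops above them.

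If uptake in this study resembled Study 304, the interval would be wider than the sample size section says. Enrolment is fixed at about 100, no minimum number of TPC recipients is set and no interim analysis is planned, so nothing in the plan would restore the 12%. A reader could therefore take 12% as assured when it depends on an unsupported assumption.

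**Working it through.** **Inputs.** N = 100, event rate p = 0.75, 95% confidence and the uptake grid come from section 9.7.2. The uptakes of 32.6% and 38.7% come from section 7.1. The 40% and 30% values are illustrative.

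**Formula.** Half-width = 1.96 × √(p(1 − p)/n), with n = 100 × uptake and p(1 − p) = 0.75 × 0.25 = 0.1875.

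**Reproducing Table 4.**

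| Uptake | n | Computed | Table 4 |
|---|---|---|---|
| 100% | 100 | 8.49% | 8.5% |
| 90% | 90 | 8.95% | 8.9% |
| 80% | 80 | 9.49% | 9.5% |
| 70% | 70 | 10.14% | 10.1% |
| 60% | 60 | 10.96% | 11% |
| 50% | 50 | 12.00% | 12% |

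All six rows agree to rounding. Wilson and exact (Clopper-Pearson) intervals give 11.7% and 12.7% at n = 50, so the table uses the simple normal approximation.

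**Testing the stated condition.** More than 50% of 100 means at least 51 recipients: 1.96 × √(0.1875/51) = 11.9%. The bound of 12% holds.

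**Below the table.**

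| Uptake | Half-width |
|---|---|
| 40% | 13.4% |
| 38.7% (Study 304, sorafenib arm) | 13.6% |
| 32.6% (Study 304, lenvatinib arm) | 14.9% |
| 30% | 15.5% |

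At 32.6% the excess over the stated bound is 14.9 − 12.0 = 2.9 percentage points. Holding 12% needs 0.1875 × (1.96/0.12)² = 50.0 recipients, which at 32.6% uptake means about 154 enrolled.

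**Is 32.6% a fair value for this study?** Four features limit the comparison.

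- It was recorded in survival follow-up, where further therapy was not part of the protocol. Here TPC is the planned second period.
- Access differed. Section 7 says sorafenib-arm subjects were eligible for "second-line studies targeting enrollment of sorafenib failures and/or sorafenib-intolerant subjects, while subjects on the lenvatinib arm were not", and section 7.1 says the trials concerned "required failure of sorafenib therapy as an entry criteria, thus precluding enrollment of lenvatinib-treated subjects in these studies".
- Study 304 was international, whereas this study runs in the US and Canada. Section 7 notes that the difference in later therapy between arms was most marked in the Western region but gives no regional rates.
- Section 7.1 describes the figure once as following progression and once as a percentage of the arm during survival follow-up, so its denominator is not fully clear. It may also include investigational drugs, which are not TPC here.

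The figure therefore works as a sensitivity value. It is not a forecast for this study.

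**The case for a change.** The strongest case for a change is that the access barrier does not obviously account for the distance to 50%. Sorafenib-arm subjects faced no such barrier, yet only 38.7% had later medication. Use of investigational drugs "in the lenvatinib arm compared with the sorafenib arm was 3.1% vs 9.5%, respectively", a gap of 6.4 points. Adding all of it to 32.6% gives 39.0%, with a half-width of 13.6%. The newer second-line drugs were approved for use after sorafenib, locoregional therapy does not count as TPC, and some subjects will be judged unsuitable. Two more table rows would cost almost nothing.

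Part of this stands. The basis for the 50% condition is not given, and uptake below one half cannot be ruled out from the documents. The 39.0% illustration is weaker. It uses a gap pooled over regions, and it leaves out the effect of a planned TPC period. It also ignores that regorafenib, named in section 7.1 among the drugs then given mostly in trials, has since been approved and could now count as commercial TPC. The 38.7% likewise comes from a setting without a planned second period.

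That a reader cannot see the precision at lower uptake is overstated. The sample size, event rate and confidence level are printed beside six rows that reproduce exactly, so the next row takes one line of arithmetic.

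**Conclusion.** No change follows. The 12% statement says what it depends on and is right when that holds. The documents do not show the condition to be false, because both lower uptake figures come from a study without a protocol TPC period.

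If uptake did fall to 32.6%, with the event rate still at 75%, the half-width would be about 15% instead of 12%. No test, threshold or decision rule uses this half-width. Section 9.7.1.8.1 already plans to report the percentage of subjects who receive TPC, and section 9.7.1.8.2 plans TEAE counts and percentages separately by treatment period. An interval computed on TPC recipients, as Table 4 is, would carry the width that their actual number gives it.

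Longer planning text would leave enrolment, conduct, analysis and interpretation as they are. Where a sensitivity table stops is a matter of presentation, and stopping this one at 50% is an acceptable choice. The conclusion assumes that the study stays descriptive and that TPC recipients are the denominator for the TPC-period rate.

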#### 9.7.3 Interim Analysis

No interim analysis is planned for this study.

#### 9.7.4 Other Statistical/Analytical Issues

Not applicable

#### 9.7.5 Procedure for Revising the Statistical Analysis Plan

If the SAP needs to be revised after the study starts, the sponsor will determine how the revision impacts the study and how the revision should be implemented. The details of the revision will be documented and described in the clinical study report.

## **11 PROCEDURES AND INSTRUCTIONS (ADMINISTRATIVE PROCEDURES)**

### **11.1 Changes to the Protocol**

Any change to the protocol requires a written protocol amendment or administrative change that must be approved by the sponsor before implementation. Amendments specifically affecting the safety of subjects, the scope of the investigation, or the scientific quality of the study require submission to health or regulatory authorities as well as additional approval by the applicable IRBs/IECs. These requirements should in no way prevent any immediate action from being taken by the investigator, or by the sponsor, in the interest of preserving the safety of all subjects included in the study. If the investigator determines that an immediate change to or deviation from the protocol is necessary for safety reasons to eliminate an immediate hazard to the subjects, the sponsor's medical monitor and the IRB/IEC for the site must be notified immediately. The sponsor must notify the health or regulatory authority as required per local regulations.

Protocol amendments that affect only administrative aspects of the study may not require submission to health or regulatory authority or the IRB/IEC, but the health or regulatory authority and IRB/IEC should be kept informed of such changes as required by local regulations. In these cases, the sponsor may be required to send a letter to the IRB/IEC and the Competent Authorities detailing such changes.

### **11.2 Adherence to the Protocol**

The investigator will conduct the study in strict accordance with the protocol (refer to ICH E6, Section 4.5).

### **11.3 Monitoring Procedures**

The CRO's CRA will maintain contact with the investigator and designated staff by telephone, letter, or email between study visits. Monitoring visits to each site will be conducted by the assigned CRA as described in the monitoring plan. The investigator will allow the CRA to inspect the clinical, laboratory, and pharmacy facilities to assure compliance with GCP and local regulatory requirements. The CRFs and subject's corresponding original medical records (source documents) are to be fully available for review by the sponsor's representatives at regular intervals. These reviews verify adherence to study protocol and data accuracy in accordance with local regulations. All records at the site are subject to inspection by the local auditing agency and to IRB/IEC review.

In accordance with ICH E6, Section 1.52, source documents include, but are not limited to, the following:

- Clinic, office, or hospital charts

- Copies or transcribed health care provider notes that have been certified for accuracy after production
- Recorded data from automated instruments such as IxRS, x-rays, and other imaging reports (eg, sonograms, CT scans, magnetic resonance images, radioactive images, ECGs, rhythm strips, EEGs, polysomnographs, pulmonary function tests) regardless of how these images are stored, including microfiche and photographic negatives
- Pain, quality of life, or medical history questionnaires completed by subjects
- Records of telephone contacts
- Diaries or evaluation checklists
- Drug distribution and accountability logs maintained in pharmacies or by research personnel
- Laboratory results and other laboratory test outputs (eg, urine pregnancy test result documentation and urine dip-sticks)
- Correspondence regarding a study subject's treatment between physicians or memoranda sent to the IRBs/IECs
- CRF components (eg, questionnaires) that are completed directly by subjects and serve as their own source

#### **11.4 Recording of Data**

A CRF is required and must be completed for each subject by qualified and authorized personnel. All data on the CRF must reflect the corresponding source document, except when a section of the CRF itself is used as the source document. Any correction to entries made on the CRF must be documented in a valid audit trail where the correction is dated, the individual making the correct is identified, the reason for the change is stated, and the original data are not obscured. Only data required by the protocol for the purposes of the study should be collected.

The investigator must sign each CRF. The investigator will report the CRFs to the sponsor and retain a copy of the CRFs.

#### **11.5 Identification of Source Data**

All data to be recorded on the CRF must reflect the corresponding source documents. For the following item(s), the data recorded directly on the CRF are to be considered source data:

- Study drug compliance (eg, the reason for any change of dosage)
- Indication for prior/concomitant medication (drug/therapy)
- Discontinuation information (eg, in the case of lost to follow-up due to the subject choice)
- Sampling date and time for the drug concentration

- Sampling date for the clinical laboratory tests
- Comments and other information on AEs (eg, severity, relationship to study drug, outcome)

## **11.6 Retention of Records**

The circumstances of completion or termination of the study notwithstanding, the investigator is responsible for retaining all study documents, including but not limited to the protocol, copies of CRFs, the Investigator's Brochure, and regulatory agency registration documents (eg, Form FDA 1572, ICFs, and IRB/IEC correspondence). The site should plan to retain study documents, as directed by the sponsor, for at least 2 years after the last approval of a marketing application in an ICH region and until there are no pending or contemplated marketing applications in an ICH region or at least 3 years have elapsed since the formal discontinuation of clinical development of the investigational product.

It is requested that at the completion of the required retention period, or should the investigator retire or relocate, the investigator contact the sponsor, allowing the sponsor the option of permanently retaining the study records.

## **11.7 Auditing Procedures and Inspection**

In addition to routine monitoring procedures, the sponsor's Clinical Quality Assurance department conducts audits of clinical research activities in accordance with the sponsor's SOPs to evaluate compliance with the principles of ICH GCP and all applicable local regulations. If a government regulatory authority requests an inspection during the study or after its completion, the investigator must inform the sponsor immediately.

## **11.8 Handling of Study Drug**

All study drug will be supplied to the PI (or a designated pharmacist) by the sponsor. Drug supplies must be kept in an appropriate secure area (eg, locked cabinet) and stored according to the conditions specified on the drug labels. The investigator (or a designated pharmacist) must maintain an accurate record of the shipment and dispensing, returns and destruction of the study drug in a drug accountability ledger, a copy of which must be given to the sponsor at the end of the study. An accurate record of the date and amount of study drug dispensed to each subject must be available for inspection at any time. The CRA will visit the site and review these documents along with all other study conduct documents at appropriate intervals once study drug has been received by the site.

All drug supplies are to be used only for this study and not for any other purpose. The investigator (or site personnel) must not destroy any drug labels or any partly used or unused drug supply before approval to do so by the sponsor. At the conclusion of the study and as appropriate during the study, the investigator (or a designated pharmacist) will return all used and unused drug containers, drug labels, and a copy of the completed drug disposition form

to the sponsor's CRA (or designated contractor) or, when approval is given by the sponsor, will destroy supplies and containers at the site.

